3.2 Study Design

This is a Phase II, single-centre, randomized, double-masked, parallel-arm, vehicle-controlled trial, designed to evaluate the preliminary efficacy and safety of rhNGF eye drops at 20 µg/ml concentration administered six times daily for 8 weeks in patients who underwent cataract and corneal refractive surgery, both known to damage the corneal sensory nerve plexus.

Eligible patients will be randomized 2:1 to either rhNGF eye drops 20 µg/ml (120 patients) or vehicle (60 patients) six times daily and treated for 8 weeks:

Group 1: rhNGF 20 µg/mL: *One drop (40 µL) corresponding to 0.80 µg of rhNGF will be instilled into each eligible eye six times a day (every 2h), for a total daily dose of 9.6 µg (both eyes, if applicable), for 56 consecutive days..*

Group 2: Vehicle: *One drop (40 µL) will be instilled into each eligible eye six times a day (every 2h).*

[figure not shown]
In all patients, both eyes will be treated, if meet the eligibility criteria. If only one eye is eligible, then only that eye will be treated.

In the 4 week follow up no further treatment is planned except artificial tears, per Investigator decision. Administration of such medications will be recorded in eCRF (number of drops per day).

Drop-Outs after randomization will not be replaced.

The study flow chart is given below:

Figure 3.2.1 Study flow chart

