3.6 Sample Size estimation

Sample size was calculated by assuming at single eye level a mean difference from baseline mean SANDE scores of -30±20 in the rhNGF groups versus -20±20 in vehicle group (80% power, alpha =0.05; 2-sided test), considering that the active comparator has already proven safe and effective in dry eye patients. The sample size has been calculated based on a 2:1 randomization by the following formula:

$$n1 = (0.5) \times n \times (1 + k)$$

$$n2 = (0.5) \times n \times (1 + (1/k))$$

with n1= active treatment and n2= vehicle and n= 63 and k= n1 /n2 = 2/1=2. Therefore n1= 94,5 and n2=47.25. Assuming a 5% drop out rate, a total of 100 patients in the active arm and 50 in the vehicle arm are required.

However, in order to provide the mean of detecting a significant difference also on a clinical sign of the effect of the rhNGF therapy (namely Co-primary Efficacy Endpoint cornea vital staining with fluorescein (National Eye Institute [NEI] scales)), sample size calculation was also performed by assuming, at single eye level, a mean difference from baseline in Cornea NEI scale scores of -3.9 ± 2.2 in the rhNGF groups versus -2.9 ± 2.2 in vehicle group (80% power, $\alpha = 0.05$; 2-sided test), considering that the active comparator has already proven safe and effective in dry eye patients. The sample size has been calculated based on a 2:1 randomization by the following formula:

$$n1 = (0.5) \times n \times (1 + k)$$

$$n2 = (0.5) \times n \times (1 + (1/k))$$

with $n1 =$ active treatment and $n2 =$ vehicle and $n = 76$ and $k = n1 / n2 = 2/1 = 2$. Therefore $n1 = 114$ and $n2 = 57$. Assuming a 5% drop out rate, a total of 120 patients in active arm and 60 in the vehicle arm are required. This calculation is based on one study eye per patient. (Whereas also two study eyes per patient may occur, that will increase power to above 80%).

Considering the two calculations performed to determine the sample size, in this study will be enrolled 180 patients (120 patients enrolled in active arm and 60 in the vehicle arm) in order to detect both changes at the same time in the variables.

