7.2.7 Efficacy Variables

Primary Endpoints: SANDE Score

The Symptom Assessment in Dry Eye (SANDE) questionnaire is a short questionnaire to evaluate both dry eye intensity and frequency by using a 100 mm visual analogue scale (VAS). The patient symptoms of ocular dryness and/or irritation will be quantified on the scale based on two questions that assess both severity and frequency of symptoms.

For the assessment, the patients mark on the 100 mm VAS line the point that they feel represents their perception of their current state. The VAS score is determined by measuring in millimeters from the left hand end of the line to the point that the patient marks. The SANDE scores will be then evaluated for the 2 questions severity (0-100) and frequency (0-100).

The SANDE score will be assessed at Baseline, Week 4, Week 8 and Week 12 visit and is recorded on the eCRF page ‘Symptoms Assessment in Dry Eye’. At each visit, only one assessment is performed aggregating the situation for both eyes (i.e. no separate assessment per study eye).

Primary endpoints will be defined as:

- Change from Baseline in SANDE frequency score at Week 8
- Change from Baseline in SANDE severity score at Week 8

If at least one SANDE assessment is missing at Week 8, the values of the last post-baseline assessment (including those from unscheduled visits) with non-missing values for frequency and severity will be imputed (LOCF). No imputation is performed in case of a missing baseline value (as defined in section 7.1).

Additionally, SANDE frequency and severity scores as well as respective changes from Baseline will be evaluated without any imputation for Week 4, Week 8 and Week 12, respectively.

Co-Primary Efficacy Endpoint: Corneal Staining (NEI Scale)

As grading scale of the corneal and conjunctiva damage, the NEI/Industry Workshop guidelines will be used [2]. The cornea is divided into five sectors (central, superior, inferior, nasal and temporal), each of which is scored on a scale of 0–3, with a maximal score of 15.

Briefly, on the grading scale used grade 0 reflects normal/healthy situation, whereas grade 3 reflects a severe damage in each considered sector.

Ocular Surface Staining is assessed separately for each eye at Baseline, Week 4, Week 8 and Week 12 visit and is recorded on the eCRF page 'Ocular Surface Staining (NEI score)'.

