8.2 Specific Methods for Efficacy Analyses

As a general principle, all efficacy analyses will be performed on a patient-level, considering the Main Eye for the analysis of Co-Primary and Secondary efficacy endpoint. Efficacy data in Secondary eye will be present as descriptive summaries and listed.

For the primary and co-primary efficacy endpoints, mean change from baseline will be compared between treatment groups. The null hypothesis will be tested that there is no difference between rhNGF and vehicle in the mean overall CFB between both treatments:

$$H_0: \mu_{\text{rhNGF}} = \mu_{\text{Vehicle}}$$

$$H_1: \mu_{\text{rhNGF}} \neq \mu_{\text{Vehicle}}$$

Where μ is the mean change from baseline at considered visit within the given treatment.

This hypothesis will be tested exploratory at a 5% level of significance with an Analysis of the Covariance (ANCOVA) with treatment, respective baseline value and eye subgroup (1 vs 2 study eyes treated) in the model.

The Least-squares means estimate of the treatment effect and the treatment group difference (both with 95% confidence intervals) will be reported. P-values will be rounded to three decimal places. If a p-value is less than 0.001 it will be reported as “<0.001”. Due to the high numbers of observations, the assumption of normality is assumed.

The ANCOVA analysis will be performed for the following endpoints:

- Change from Baseline in SANDE Frequency and Severity Score at Week 8 (LOCF) for the FAS as exploratory primary efficacy analyses
- Change from Baseline in SANDE Frequency and Severity Score at Week 8 (LOCF) for the PPS as supportive to primary efficacy analyses

- Change from Baseline in SANDE Frequency and Severity Score (without imputation) at Week 8 for the FAS as supportive to primary efficacy analyses
- Change from Baseline in Corneal Staining at Week 8 (LOCF) for the FAS as exploratory to co-primary efficacy analyses
- Change from Baseline in Corneal Staining at Week 8 (LOCF) for the PPS as supportive to co-primary efficacy analyses
- Change from Baseline in Corneal Staining (without imputation) at Week 8 for the FAS as supportive to co-primary efficacy analyses

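### The SAP's large-sample argument for its ANCOVA covers normality but not unequal spread under 2:1 allocation; pre-specifying a robust standard error would be a cheap safeguard

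*SAP*

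**What the plan says.** SAP 3.2 sets the allocation: "Eligible patients will be randomized 2:1 to either rhNGF eye drops". SAP 3.6 gives the sizes as "120 patients enrolled in active arm and 60 in the vehicle arm".

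SAP 8.2 fits an ANCOVA with treatment, the baseline value and the number of study eyes (one or two). "This hypothesis will be tested exploratory at a 5% level of significance". Least-squares means and their difference are reported with 95% intervals. The model applies to three outcomes (SANDE frequency, SANDE severity, corneal staining), each in three versions (FAS with LOCF, PPS with LOCF, FAS as observed), so nine fits. SAP 9.5.1 and 9.5.2 add separate fits by eye subgroup if that factor is significant.

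The one sentence on assumptions is "Due to the high numbers of observations, the assumption of normality is assumed". Neither document mentions equal variances, arm-specific variances, a robust standard error or a sensitivity analysis for unequal spread. SAP 8.1 tabulates SDs by group, but nothing in the analysis depends on them.

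The only SDs in the plan are the planning values in SAP 3.6, equal in both arms: "a mean difference from baseline mean SANDE scores of -30±20 in the rhNGF groups versus -20±20 in vehicle group" and "scores of -3.9 ± 2.2 in the rhNGF groups versus -2.9 ± 2.2 in vehicle group".

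**The concern.** An ANCOVA with no variance structure named ordinarily uses one residual variance pooled over both arms. That is an inference from the wording, since the SAP does not state it. With equal arms, a pooled variance gives nearly the right standard error for the difference even if the spreads differ. With 2:1 allocation it does not: the pooled variance is dominated by the larger rhNGF arm, while the uncertainty of the difference is dominated by the smaller vehicle arm. The interval is too narrow if vehicle is the more variable arm and too wide if rhNGF is.

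There is a plausible route to unequal spread. Both scales stop at zero. SANDE runs from 0 to 100, and for corneal staining there are five sectors, "each of which is scored on a scale of 0–3, with a maximal score of 15". The plan expects larger falls on rhNGF, so more rhNGF patients may reach the floor and that arm's spread may shrink. What is at stake is the calibration of the only between-arm intervals and p-values planned, since SAP 9.5.3 plans no inference for the secondary endpoints.

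**Working it through.** **Plan's own figures.** The inputs from SAP 3.6 are "80% power, alpha =0.05; 2-sided test", differences of 10 and 1.0, and SDs of 20 and 2.2. Per arm at 1:1, n = 2(1.960 + 0.842)² × SD² / difference².
- SANDE: 62.8, so 63. At 2:1, 0.5 × 63 × 3 = 94.5 and 0.5 × 63 × 1.5 = 47.25.
- Corneal staining: 75.98, so 76. At 2:1, 0.5 × 76 × 3 = 114 and 0.5 × 76 × 1.5 = 57. With 5% dropout, 114/0.95 = 120 and 57/0.95 = 60.

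These reproduce the SAP. The sample size is not in question here.

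**Effect of unequal spread.** Let r be the vehicle SD divided by the rhNGF SD, with the rhNGF SD set to 1. Then

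q = pooled SE / true SE = √{[(113 + 56r²)/169] × (1/114 + 1/57)} / √(1/114 + r²/57),

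and coverage is approximately 2Φ(1.96q) − 1. For r = 1.5:
- pooled variance = (113 + 126)/169 = 1.414
- squared pooled SE = 1.414 × 0.02632 = 0.03722
- squared true SE = 0.00877 + 0.03947 = 0.04825
- q = √(0.03722/0.04825) = 0.878, so coverage is 91.5%.

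The ratios r are assumptions, because the documents give none other than 1. The SAP's model was also simulated at 114/57, with 20,000 trials per ratio in the largest sets of runs:

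| r (assumed) | q | Coverage, formula | Coverage, simulated ordinary ANCOVA |
|---|---|---|---|
| 0.8 | 1.076 | 96.5% | 96.3-96.7% |
| 1.0 | 1.000 | 95.0% | 94.9-95.2% |
| 1.25 | 0.929 | 93.1% | 93.0-93.6% |
| 1.5 | 0.878 | 91.5% | 90.9-91.6% |

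With HC3 standard errors, simulated coverage stayed between 94.5% and 95.6% throughout.

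**Sample size does not help; the allocation is the cause.** For large 2:1 trials q² tends to (2 + r²)/(1 + 2r²), which does not contain n. At r = 1.5 this is 4.25/5.5 = 0.773, so q = 0.879. The formula error rate is 8.5% at 114/57, at 1140/570 and at 11400/5700. At 86/86 it is 5.0% (simulated 4.8%).

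**How much spread could the floor create?** The planned changes and SDs were simulated with truncation at zero. The baseline means are assumptions: staining 4 to 8 and SANDE 40 to 70.
- At the planned effects, r was about 1.02 to 1.15 and pooled coverage 93.9% to 95.1%.
- With no treatment effect, r was 1.00 and coverage 94.5% to 95.3%. Both arms then meet the same floor.

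**Cost of HC3 when spreads are equal.** Ignoring covariates, HC3 replaces 1/n by 1/(n − 1) in each arm. So √[(1/113 + 1/56)/(1/114 + 1/57)] = √(0.02671/0.02632) = 1.007. With the two covariates the simulated increase is about 1%. In small arms HC3 is somewhat conservative: coverage is about 96-97% at 10/5, 96.0% at 16/8 and 95.8% at 30/15.

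**The case against.** The case against acting is substantial, and most of it stands.

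- **No evidence of unequal spread.** The planning SDs are equal. Ratios of 1.25 and 1.5 are hypothetical, and the simulations built on the plan's own effects lose about one coverage point at most.
- **Flooring does not create false positives.** A reader might infer from the r = 1.5 row that the trial's 5% test really runs at about 8.5%. The documents do not support that. The floor separates the spreads only when rhNGF works better than vehicle. Inflation under no mean effect would need a drug that changes variance without changing the mean, and nothing in the documents suggests this.
- **The direction is open.** A mix of responders and non-responders on rhNGF would widen the larger arm and make the ordinary interval too wide. Calling the planned intervals too narrow would be unjustified.
- **The inference is exploratory.** SAP 3.7 and 8.2.1.3 say so, and no pre-specified decision turns on a coverage point. Arm SDs will be visible in the tables.
- **The normality sentence claims only normality.** That is reasonable at about 170 patients.

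Two things remain. The exploratory label waives multiplicity control, but it does not make a miscalibrated interval correct. And if unequal SDs are noticed only after unmasking, the choice of variance method becomes data-driven.

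**Conclusion.** The point holds as a minor, low-cost improvement. The SAP's stated support for its ANCOVA leaves unequal spread unaddressed, and under 2:1 allocation a larger sample would not remove the problem. Whether the spreads will differ is unknown. The expected loss from flooring at the planned effects is about one coverage point or less, and this rests on assumed baseline distributions. The drop to about 93% or 91-92% requires assumed SD ratios of 1.25 or 1.5, which the documents neither support nor exclude. All the figures take the ordinary single-variance ANCOVA as what the SAP intends. The treatment estimate and the sample size are unaffected.

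**What to change.** In SAP 8.2, before unmasking, keep the ANCOVA model and its point estimate, and state that the standard error, 95% interval and p-value for the treatment difference use the HC3 heteroscedasticity-consistent estimator with the model's residual degrees of freedom. Apply this to all nine listed FAS and PPS fits. Name this one method, so that no choice remains once the arm SDs are seen.

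For any repeats by eye subgroup with small arms, report the ordinary model-based interval alongside, because HC3 is somewhat conservative there. The normality sentence may stay, but it should not be read as covering equal variances.

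The cost is a sentence or two in the SAP, a small programming change, and a standard error about 1% larger at 114/57 if the spreads turn out equal.

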8.2.1 Statistical/Analytical Issues

8.2.1.1 Adjustments for Covariates

Not alpha adjustment is envisaged, as all statistical hypotheses testing will be performed in an exploratory manner.

8.2.1.2 Handling of Dropouts or Missing Data

In the derivation of endpoints there will be no replacement of missing data except for primary endpoint CFB in SANDE Frequency and Severity Score and co-primary efficacy endpoint CFB in Corneal Staining, age, adverse event dates as well as concomitant medication dates. Details of applied imputations are described in the respective sections of chapter 7.2.

8.2.1.3 Multiple Comparisons/Multiplicity

Due to this being an exploratory study, no adjustment of any p-values will be made to account for inflation of the Type 1 error rate arising from multiple comparisons or multiple endpoint testing.

8.3 Specific Methods for Safety Analyses

As a generally principle, adverse event data will be analyzed separately by study period (Non-TEAE, TEAE).

All other safety assessments will be summarized by Visit and Eye (Main Eye/Secondary Eye).

According to the study protocol, both eyes of a patient should be treated, if eligible. However, there might be the situation, that one eye will not be treated. If a visit-based safety assessment was performed in an eye, which has not been treated with study medication, it will not be included in descriptive summaries but displayed in listings. Such assessments will be flagged in the listings accordingly.

9 Overview of Tables, Listings and Figures

This section describes the TLFs per topic with variables and populations used. For the content, titles and layout of tables see the table shells, which will be added as appendix to this document.

9.1 Disposition of Patients

A disposition summary of patients includes the number (n) and percentage (%) of patients screened, screen failures, included in the Enrolled Set, included in the SAF, FAS as well as in the PPS as defined in section 6.1. Presentation will be provided by study treatment and overall. Percentages, if applicable, will be based on the total number of patients (of considered treatment group) included in the Enrolled Set. A listing will also be provided for this information on individual patient level for the Enrolled Set.

A summary of study discontinuation will be provided for the Enrolled Set including number and percentage of discontinuations study during treatment period, primary reason for study discontinuation during treatment period, discontinuations during the Follow-Up period, primary reason for study discontinuation during the Follow-Up Period as well as study completers. Moreover, number and percentages of patients who were unmasked during study will be provided. Presentation will be provided by study treatment and overall. Percentages will be based on the total number of patients (of considered treatment group) included in the Enrolled Set.

A listing will also be provided for this information added by the date of first and last study medication intake as documented on the eCRF page ‘Study Drug Dosing Dates’.

For Screen failure a listing will be provided including the primary reason for discontinuation.

9.2 Protocol Deviations and Patient Eligibility

Protocol Deviations that might affect the efficacy of treatment will be reviewed during BDRM. A major protocol deviation will lead to an exclusion from the PPS.

The number of patients in the FAS who had at least one Major Protocol Deviation as well as a specific type of protocol deviation (as defined during the BDRM) will be summarized by absolute counts (n) and percentages (%) and displayed by treatment group and overall. Percentages will be based on the number of patients in the FAS.

A listing will be provided presenting all protocol deviation data for the Enrolled Set.

The eligibility of all patients for entry into the study will be assessed at the Baseline visit by the inclusion and exclusion criteria (‘Inclusion Criteria’ and ‘Exclusion Criteria’ eCRF pages). Two listing will be presented including all patients of the Enrolled Set, who fail/meet at least one Inclusion or Exclusion criteria, along with all their deviating Inclusion and Exclusion responses, respectively.

9.3 Demographic and Other Baseline Characteristics

9.3.1 Demographic Characteristics

Demographic data age, gender, ethnicity as well as race will be summarized by treatment group and overall for the SAF by treatment group and overall. Demographic Data will also be listed.

9.3.2 History of Corneal surgery and other Medical History

Summary statistics will be provided for patients with previous cataract surgery and involved eyes per patient, patients with previous refractive surgery and involved eyes per patient and patients with previous LASIK surgery and involved eyes per patient as well as identified Study Eyes per patient ('Left Eye only', 'Right Eye only', 'Both Eyes') and Identified Main Eye ('Left Eye', 'Right Eye' as defined in section 6.1) by treatment group and overall for patients in the SAF. A listing will also be provided.

Other Medical History will be summarized for the SAF by treatment group and overall on a per-patient basis (i.e. if a patient reported the same event repeatedly the event will be counted only once at the specific level of display). Absolute counts (n) and percentages (%) will be presented for the number of patients with at least one Medical History event, and per SOC and per PT within SOC.

A listing presents all medical history data for the SAF.

9.3.3 Prior and Concomitant Medications

Prior and Concomitant Medications will be summarized for the SAF on a per-patient basis (i.e. if a patient reported the same medication repeatedly the medication will be counted only once at the specific level of display). Absolute counts (n) and percentages (%) will be presented for the number of patients with at least one medication, and per WHO-ATC Drug Class 2 (ATC therapeutic main class) and per WHO-DD Drug Name (Preferred Term) within WHO-ATC Drug Class 2.

A Listing will be presented for Prior and Concomitant medications of patients in the SAF providing all collected details on the eCRF.

9.4 Measurements of Exposure and Treatment Compliance

Exposure will be evaluated by summary statistics for the parameters Treated Eyes and Treatment Duration by treatment group. This analysis will be performed for the SAF. This information will be listed.

Compliance will be summarized categorical (<80%, 80-120%, >120%) for the FAS by treatment group. This information as documented on the eCRF Page 'Study Drug Dosing and Accountability' will be listed for the SAF accordingly.

Further information on compliance as recorded on the eCRF Page 'Diary Information' and 'Exposure' at Week 4 and Week 8 will be listed for the SAF.

Further information on compliance as recorded on the eCRF Page 'Patient Diary' at Week 4 and Week 8 will be listed for the SAF.

9.5 Efficacy Results

9.5.1 Primary Efficacy Analysis

Results of the SANDE Frequency and SANDE Severity Score at Week 8 (absolute values as well as changes from baseline) will be summarized descriptively by treatment group. For the primary analysis LOCF is applied as described in section 7.2.7. The exploratory p-value and estimates for treatment effect as well as treatment group difference resulting from the ANCOVA analysis specified in section 8.2 will be reported in addition for Week 8 Visits. Primary analysis will be performed on the FAS.

For supportive purposes, this analysis of Week 8 results will be repeated for the PPS to investigate the effect of protocol deviations on the results.

If the covariate ‘Number of Study Eyes’ would result in a significant effect, the ANCOVA analysis will be repeated for each subgroup separately.

A similar analysis will be performed for the SANDE Frequency and SANDE Severity Score (without imputation) at Week 8. This analysis will be performed for the FAS only.

A descriptive analysis will be performed for the SANDE Frequency and SANDE Severity Score (without imputation) at Baseline, Week 4 and Week 12 as well as respective CFB without performing statistical inference. This analysis will be performed for the FAS only. All data on SANDE Scores will be listed on the FAS, indicating clearly imputed values.

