3.7 Changes in the Conduct of Study or Planned Analysis compared to protocol/CIP

This SAP implements the subsequent deviations and clarifications from the analysis specification of the study protocol:

- For the SAP, study endpoints are presented as provided in the protocol synopsis and protocol section 2 (study objectives).
- Definition of Screen Failures. In the study protocol (section 10.1.1) a screen failure is defined as patient who is not eligible, i.e. is not respecting all the inclusion/exclusion criteria. According to the study protocol, such patients should not be randomized and enrolled.
To streamline presentation of patient flow for reporting and to extend definition also for protocol deviations, screen failure will be defined as screened patients, who are not randomized. By this, patients, who were randomized although they did not comply with eligibility criteria will not be considered as screen failure. On the contrary, patients, who comply with all eligibility criteria but dropped out from the study before randomization (e.g. due to consent withdrawal) will be considered as screen failure.
- Definition of compliance: in section 10.3, the study protocol demands further compliance definitions based on diary card information to investigate compliance with study eye treatment. However, as no eye-specific assessments were recorded on diary card, no such definitions were established.
- In the study protocol, no inferential analyses are specified. However, purely exploratory 95% confidence intervals and hypothesis testing for the difference between treatment groups will be implemented in the SAP on sponsor's request. These inferential procedures will be purely exploratory without adjusting for type I error rate.

4 General Definitions

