6.1 Analysis Sets

A patient will be defined as *screened* after the signature of the informed consent, regardless of the completion of all the screening procedures. A patient will be defined as screen failure, if he was screened but not enrolled in the study.

Enrolled Set:

A patient will be defined as *enrolled* in the study if he/she is randomized. This analysis set will be used for presentation of study disposition.

If not stated otherwise, analyses based on the Enrolled Set will be summarized by the treatment randomized.

Safety Set (SAF):

The Safety Set will be defined as all enrolled patients who receive at least one dose of the investigational medicinal product (IMP) at the study eye(s). *This analysis set will be used for the demographic, baseline and background characteristics and safety analysis.* All analyses based on the SAF will be summarized by the treatment received.

Full Analysis Set (FAS):

The Full Analysis Set will be defined as all patients in the SAF, who have at least one post-baseline efficacy measurement in a study eye. This analysis set will be used for the primary and co-primary efficacy analysis and all other efficacy analyses. All efficacy analyses based on the FAS will be summarized by the treatment randomized.

Per Protocol Set (PPS):

The Per Protocol Set will be defined as *all patients in the FAS who fulfill the study protocol requirements in terms of investigational medicinal product intake and collection of primary and co-primary efficacy data and with no major deviations that may affect study results.* This analysis set will be used for supportive efficacy analysis. All efficacy analysis based on the PPS will be summarized by the treatment randomized.

Each patient could either have 1 or 2 study eyes eligible for the analysis. For each patient a main (study) eye will be identified to enable a patient based presentation of analysis.

For patients with only 1 study eye (i.e. treated eye), this eye will be defined as 'Main Eye'.

For patients with 2 study eyes, the study eye with the higher corneal staining score at baseline will be considered as 'Main Eye' unless corneal staining score is not available at Week 8 Visit for this eye.

In this case, the other eye will be considered as 'Main Eye'. If both eyes are equally worse, the right eye will be the 'Main Eye'.

The eye not selected as 'Main Eye', will be called 'Secondary Eye'.

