6.2 Subgroup Definitions

For supportive efficacy analysis, subgroup of patients with '1 study eye only' vs. '2 study eyes' will be utilized.

7 Definition of Time Points and Analysis Variables

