9.6.5 External Ocular Examinations

All evaluations of the motility of extraocular muscle Right and Up, Right, Right and Down, Left and Up, Left, Left and Down will by will be summarized descriptively by treatment group and study visit for the Main Eye as well as the Secondary Eye. This analysis will be performed on the SAF. These data will also be listed.

Incidences of proven eyelid deformity/abnormality, abnormal motor function of eyelids, corneal exposure in case of closed eyelid, proven punctual occlusion, punctual plugs, thermal or surgical occlusion or other punctual occlusion will be presented by treatment group and study visit for the Main Eye as well as for the Secondary Eye.

Incidences will be calculated as number and percentages of affected patients. The analysis will be performed on the SAF. Moreover, these date will be listed.

10 References

1. Holladay, JT (1997) Proper Method for Calculating Average Visual Acuity. *Journal of Refractive Surgery*, 13, pp. 388-391.
2. Lemp MA. Report of the National Eye Institute/Industry Workshop on clinical trials in dry eye. *CLAO J*1995, 21(4):221–32.

11 Tables, Listings and Figures

Details on Tables and Listings (TLFs) will be provided in a separate document and are attached as appendix to this SAP.

TLF Number	Title
List of Tables	
Table 14.1-1.1	Summary of Patient Disposition
Table 14.1-1.2	Summary of Study Discontinuation (Enrolled Set)
Table 14.1-2.1	Summary of Protocol Deviations (FAS)
Table 14.1-3.1	Summary of Demographic Data (Enrolled Set)
Table 14.1-4.1	Summary of History of Corneal Surgery (SAF)
Table 14.1-5.1	Summary of Medical History (SAF)
Table 14.1-6.1	Summary of Prior Medications (SAF)
Table 14.1-6.2	Summary of Concomitant Medications (SAF)
Table 14.1-7-1	Summary of Treatment Compliance (FAS)
Table 14.2-1.1	Summary of SANDE Scores at Week 8 (LOCF) (FAS)
Table 14.2-1.2	Summary of Change from Baseline of SANDE Scores at Week 8 (LOCF) (FAS)
Table 14.2-1.2.1	Summary of Change from Baseline of SANDE Scores at Week 8 in Subgroups (LOCF) (FAS)
Table 14.2-1.3	Summary of SANDE Scores at Week 8 (LOCF) (PPS)
Table 14.2-1.4	Summary of Change from Baseline of SANDE Scores at Week 8 (LOCF) (PPS)
Table 14.2-2.1	Summary of SANDE Scores by Visit (Observed) (FAS)
Table 14.2-2.2	Summary of Change from Baseline of SANDE Scores by Visit (Observed) (FAS)
Table 14.2-3.1	Summary of Corneal Staining at Week 8 (LOCF) (FAS)

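### The trigger for separate ANCOVAs by number of study eyes tests a difference in mean change, not a difference in treatment effect

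*SAP*

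**What the plan says.** SAP section 8.2 compares the arms on change from baseline at Week 8 by an ANCOVA "with treatment, respective baseline value and eye subgroup (1 vs 2 study eyes treated) in the model". These three terms enter additively. The model serves SANDE frequency, SANDE severity and corneal staining in the Main Eye.

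Sections 9.5.1 and 9.5.2 add the same conditional rule for the primary and co-primary endpoints: if the number-of-eyes covariate "would result in a significant effect, the ANCOVA analysis will be repeated for each subgroup separately". No significance level is given for this trigger. I take it as the two-sided 5% used in section 8.2.

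The purpose of the repeat is not stated. Section 6.2 says only that the one-eye and two-eye subgroups serve supportive efficacy analysis. Section 3.7 says of all the testing: "These inferential procedures will be purely exploratory without adjusting for type I error rate". The table list in section 11 includes subgroup summaries of Week 8 change (Tables 14.2-1.2.1 and 14.2-3.2.1) without repeating the condition. Their shells are in a separate document.

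**The concern.** In an additive model the eye-subgroup coefficient is the difference in mean change between two-eye and one-eye patients, averaged over the arms. Its p-value does not test whether the rhNGF-minus-vehicle difference varies with the number of eyes. Yet what the rule releases, an ANCOVA within each subgroup, is a pair of rhNGF-minus-vehicle differences. The condition and the output concern different parameters.

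Readers have reason to ask the question. Number of study eyes is the only subgroup factor the SAP defines, and for SANDE "only one assessment is performed aggregating the situation for both eyes", so one symptom score may reflect one or two treated eyes. Under the rule, whether the subgroup ANCOVAs are run depends on a prognostic difference. If they are run, the fact that the trigger fired may be read as evidence that the drug works differently in the two groups.

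**Working it through.** **Inputs.** From SAP section 3.6: SANDE change −30 versus −20 with SD 20; corneal staining change −3.9 versus −2.9 with SD 2.2; two-sided alpha 0.05; 80% power; 2:1 allocation; 5% dropout. Assumed, because the documents are silent: two-eye share s of 30%, 50% or 70%, and every one-eye/two-eye gap below.

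**The plan's own figures.** With n = 2[SD(1.960 + 0.842)/δ]², SANDE gives 62.8, rounded to 63, and staining 76.0, rounded to 76. At k = 2, 0.5 × 76 × 3 = 114 and 0.5 × 76 × 1.5 = 57; dividing by 0.95 gives 120 and 60. These agree with the SAP. I use 114 and 57 evaluable patients, 171 in all.

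**What the trigger estimates.** Let g be the two-eye minus one-eye gap in mean change on vehicle, and d the difference in treatment effect between the subgroups. With allocation independent of eye number, the additive coefficient estimates g + (114/171)d = g + (2/3)d. It mixes the two quantities and cannot separate them.

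**Firing rate, SANDE, same 10-point effect in both subgroups (d = 0).** SE = 20·√[1/(171s) + 1/(171(1−s))], which is 3.059 at s = 50% and 3.338 at 30% or 70%. For a 10-point gap, 10/3.338 = 3.00 gives 85% and 10/3.059 = 3.27 gives 90.5%. Simulation without a baseline term (4,000 trials per cell) agrees:

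| Gap in mean change | s = 30% | s = 50% | s = 70% |
|---|---|---|---|
| 0 | 4.7% | 5.5% | 4.6% |
| 2 | 9.3% | 10.3% | 9.3% |
| 5 | 31.0% | 36.5% | 31.5% |
| 10 | 85.0% | 90.2% | 83.4% |

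A treatment-by-eyes test rejects in 4.6–5.2% throughout. With the SAP's baseline term added (assumed baseline–change correlation 0.3 or 0.5), the four rows become 4–5%, 9–12%, 34–48% and 86–96%, and the interaction test 4–6%.

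**Staining, same 1-point effect, no baseline term.** For gaps of 0, 0.2, 0.5 and 1.0 points the rule fires in 5%, 8–9%, 27–31% and 77–84%.

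**Worse-eye selection.** In two-eye patients "the study eye with the higher corneal staining score at baseline will be considered as" the Main Eye, subject to a Week 8 availability exception, so their baseline staining will tend to be higher. Simulated at s = 50% (assumed baseline SD 2.2, inter-eye correlation 0.3 or 0.6, slope of change on baseline 0.3 or 0.6), a gap arising only from this selection fires the rule in 11–47% without the baseline term but 5–6% with it. The SAP's model therefore handles this mechanism. A further gap of 0.5 or 1.0 point unrelated to baseline still fires it in 32–44% or 85–95%.

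**When treatment effects do differ.**
- SANDE effects of 5 and 15, equal vehicle means: the coefficient is (2/3) × 10 = 6.67 in size; 6.67/3.338 and 6.67/3.059 give about 51–59%, and simulation 49–57%. The interaction test rejects in 28–33%.
- Effects differing by 20, with vehicle means offset by (2/3) × 20 = 13.3 so that there is no average gap: the rule fires in about 5%, the interaction test in 79–86%.

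**Precision of the alternative.** Interaction SE = SD·√(sum of 1/n over the four cells). SANDE: 6.49 to 7.08, so the 95% half-width is 12.7–13.9 and power for a 10-point interaction is 34% down to 29%. Staining: 0.71 to 0.78, half-width 1.4–1.5, power for 1 point 29% down to 25%. Within a subgroup holding share s, SE = 20·√[1/(114s) + 1/(57s)], which gives half-widths of 7.6 (70%) to 11.6 (30%) SANDE points; multiplying by 2.2/20 gives 0.8–1.3 staining points.

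**The case against.** The SAP never says the repeat is meant to detect a differing treatment effect, so the rule contradicts nothing stated. All inference is exploratory and no primary estimate changes. The two listed subgroup tables carry no condition and may already show change by arm within subgroup. The high firing rates need a gap as large as the whole planned drug effect, and the one mechanism for a gap found in the documents, worse-eye selection, is absorbed by the baseline term. The rule also responds to some real differences in treatment effect, in one scenario more often than an interaction test does.

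Much of this stands, and it limits the weight of the point. The purpose is unstated, the table contents cannot be checked, and the gaps are assumptions. Three things remain. If the aim were only to allow for a difference in mean change, the covariate already does so and no subgroup repeat is needed. The only subgroup ANCOVAs that the SAP text describes are conditional. When the rule does respond to a differing effect, it does so through g + (2/3)d, so a reader cannot tell that case from a purely prognostic gap.

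**Conclusion.** The concern holds. The rule makes subgroup treatment estimates depend on a test of another parameter. With identical SANDE effects it fires in 31–37% of trials for a 5-point gap in mean change and 83–90% for a 10-point gap. With effects differing by 20 points and no average gap, it fires in about 5%. These figures rest on 114 and 57 evaluable patients, normal outcomes, the section 3.6 SDs, a 5% trigger level, and assumed two-eye shares and gaps; at a 2-point gap the rate is only 9–10%. The overall primary and co-primary estimates are not affected. The consequence is limited to which subgroup results are produced and how they are read, but the rule should be corrected before unmasking.

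**What to change.** In SAP sections 9.5.1 and 9.5.2, replace the trigger sentence with:

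> As a supportive analysis on the FAS (LOCF), the section 8.2 model will be fitted with an added treatment-by-number-of-study-eyes term. The interaction estimate with 95% CI, and the rhNGF minus vehicle difference with 95% CI in each subgroup, will be reported regardless of the significance of any term. These results are descriptive.

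Report these in Tables 14.2-1.2.1 and 14.2-3.2.1, after checking that their shells have room for the estimates. Keep the section 8.2 model without interaction for the main estimates. Do not use the interaction p-value as a new gate; its power is too low.

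The cost is one replaced passage in each of two sections and three supportive models (SANDE frequency, SANDE severity, corneal staining), with no new data. The change removes selective reporting. It is unlikely to settle whether the effect depends on the number of eyes, because the SANDE interaction interval extends more than 12 points either side, which is why the descriptive label is needed.
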